### 1.3.4 Collection of blood samples, for patients who continue pembrolizumab after discontinuation of nantilkefusp alfa

All attempts should be made to collect the samples on time.

Cycle	From cycle 1	End of treatment
Day	1	
Pembrolizumab administration 	X	
Hematology	X 	X
Biochemistry	X 	X
Coagulation	X 	X
TSH, T3 or free T3, free T4	X 	X

1. Time to be recorded
2. Before pembrolizumab administration
3. Every other cycle

*T3, triiodothyronine; T4, thyroxine; TSH, thyroid stimulating hormone*

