1. Criteria for discontinuation of study interventions are listed in section 7.1. In case nanrilkefusp alfa needs to be discontinued for reasons other than disease progression, pembrolizumab treatment can continue for up to a total of 35 administrations (approximately 2 years) in patients without disease progression or unacceptable toxicity. A schedule of activities for patients who continue pembrolizumab after discontinuation of nanrilkefusp alfa is shown in section 1.3.2. In case pembrolizumab needs to be discontinued, nanrilkefusp alfa treatment can continue until disease progression or unacceptable toxicity and the schedule of activities for patients receiving nanrilkefusp alfa combined with pembrolizumab will apply (not applicable in the Czech Republic). In the Czech Republic: In case pembrolizumab needs to be discontinued, nanrilkefusp alfa treatment will be discontinued as well.
2. No study-specific procedures are to be performed before ICF signature.
3. Age at screening and gender
4. Primary tumor location, histology/cytology, initial diagnosis date, lines of previous treatment, start and stop dates of the treatments before this study, any prior mutations/genetic analysis (e.g., EGFR, ALK mutations), and the date of the latest disease progression if not coinciding with the stop date
5. Before nanrilkefusp alfa administration
6. Every 30 ( $\pm 2$ ) days until 120 ( $\pm 2$ ) days after the last dose of pembrolizumab or 30 ( $\pm 2$ ) days after the last dose of nanrilkefusp alfa, whichever is later
7. Before nanrilkefusp alfa administration and afterwards as clinically required
8. Follow-up visits 30 ( $\pm 2$ ) days and 90 ( $\pm 2$ ) days after the last dose of nanrilkefusp alfa and/or pembrolizumab (whichever occurs later)
9. Before and after nanrilkefusp alfa administration as described in section 8.2.3
10. In case of proteinuria  $\geq 100$  mg/dL at screening, a 24-hour urine analysis will have to be performed (before the start of nanrilkefusp alfa treatment) to document 24-hour proteinuria levels and a urine test will continue during the treatment period. In case of increase of proteinuria with  $\geq 300$  mg/dL (at any time), a 24-hour urine analysis will be performed.
11. Using either echocardiography or MUGA; the method chosen needs to stay the same throughout the trial

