### 1.3.3 Collection of blood samples, nanrilkefusp alfa combined with pembrolizumab

All attempts should be made to collect the samples on time.

Cycle	Screening	Cycle 1						Cycle 2					Cycle 3				From cycle 4				End of treatment
		1	2	6	8	9	13	1	2	6	8	9	1	2	8	9	1	2	8	9	
Nanrilkefusp alfa administration 		X	X		X	X		X	X		X	X	X	X	X	X	X	X	X	X	
Pembrolizumab administration 		X						X					X				X				
Serum for nanrilkefusp alfa PK													See section 1.3.5								
Serum for cytokines 		X	X		X	X		X	X		X	X									
Serum for nanrilkefusp alfa immunogenicity 		X						X									Cycle 4 only				X
Serum for pembrolizumab PK 		X						X									Cycles 4 and 8 only				X
Serum for pembrolizumab immunogenicity 		X						X									Cycle 4 only				X
Whole blood for RNA and DNA analysis 		X		X				X		X											
HIV, HBV, and HCV	X																				
Hematology (full complete blood count including absolute lymphocyte count)	X	X 	X 	X	X 	X 	X	X 		X	X 		X 		X 		X 		X 		X
Biochemistry (including C-reactive protein)	X	X 	X 	X		X 	X	X 		X		X 	X 		X 		X 		X 		X
Creatinine clearance	X	X 		X		X 		X 		X		X 	X 		X 		X 		X 		
C-reactive protein				X 					X 		X 										
Coagulation	X	X 		X 				X 		X 			X 		X 		X 		X 		X
TSH, T3 or free T3, free T4	X	X 											X 				X 				X
Patients with mCRPC: PSA, alkaline phosphatase, lactate dehydrogenase, CTCs, circulating tumor DNA fraction	X		X 										X 				X 				
Serum pregnancy	X																				

1. Time to be recorded
2. Time to be recorded; pembrolizumab will be administered within 30 minutes following nanrilkefusp alfa administration.
3. Before nanrilkefusp alfa administration and 4 hours ( $\pm 30$  min) after nanrilkefusp alfa administration
4. Within 1 day before nanrilkefusp alfa administration

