### **8.7 Immunogenicity assessments**

Samples for ADAs will be collected to assess nanrilkefusp alfa tolerability, correlation with PK, and potential AEs associated with ADAs against nanrilkefusp alfa and for the prediction of nanrilkefusp alfa ADA production.

Samples for pembrolizumab ADAs will be collected. These samples will be stored and a decision about their analysis will be taken at a later date.

Instructions on sample collection, handling, storage, and shipment of samples is detailed in the study-specific Laboratory Manual provided to the study site.

Samples may be stored for a maximum of 20 years (or according to local regulations) after the end of the study at a facility selected by the sponsor to enable further analysis of immune responses to nanrilkefusp alfa in combination with pembrolizumab.

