- Time to confirmed PSA progression

Time to confirmed PSA progression is defined as the time from the first day of study treatment to the date of PSA progression and will be summarized using Kaplan-Meier estimates for the mCRPC indication.

PSA progression is defined as the date when an increase of 25% or more and an absolute increase of 2 ng/mL or more from the nadir are documented. For patients who have a decline in PSA during treatment, PSA progression must be confirmed by a second value 3 or more weeks later increased with respect to the nadir PSA.

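### After a switch to pembrolizumab alone, the blood schedule has no PSA, CTC or nanrilkefusp alfa ADA sample, so four secondary endpoints are no longer measured from that point although none is defined to stop there

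*Protocol*

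**What the plan says.** **The switch.** Protocol 7.1 and footnote 1 of 1.3.1 allow a patient who stops nanrilkefusp alfa for a reason other than progression to stay on study treatment: "pembrolizumab treatment can continue for up to a total of 35 administrations (approximately 2 years"). The footnote adds: "A schedule of activities for patients who continue pembrolizumab after discontinuation of nanrilkefusp alfa is shown in section 1.3.2". The matching blood table is 1.3.4, headed "Collection of blood samples, for patients who continue pembrolizumab after discontinuation of nantilkefusp alfa" (spelling as printed). Its rows are hematology, biochemistry, coagulation and "TSH, T3 or free T3, free T4".

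**What 1.3.3, the combination schedule, collects in addition.**
- "Patients with mCRPC: PSA, alkaline phosphatase, lactate dehydrogenase, CTCs, circulating tumor DNA fraction": screening, cycle 1, cycle 3 day 1, then every other cycle from cycle 4. There is no End of treatment draw.
- "Serum for nanrilkefusp alfa immunogenicity": day 1 of cycles 1, 2 and 4, each taken within a day before the nanrilkefusp alfa dose, and End of treatment.

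**Endpoints.** Protocol section 3 lists CTC conversion, confirmed PSA decline of at least 50%, time to confirmed PSA progression and nanrilkefusp alfa ADA as secondary endpoints. SAP 10.13.10 and 10.13.11 count a CTC or PSA response at any time after baseline. SAP 12.7.9 requires a PSA response to be confirmed at least 4 weeks later and otherwise counts the patient as a non-responder. SAP 12.7.8 counts missing CTC data as non-response. SAP 6.1 takes the PSA time points from Protocol 1.3.3 alone.

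**The concern.** The endpoints run from first dose with no stop at the switch, but the samples behind them do stop. Patients who switch are still on study treatment and, under 1.3.2, still have tumor scans every 6 weeks.

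The loss is not neutral. Under the non-responder rules, an absent PSA or CTC value becomes a failure. For ADA, Protocol 8.7 wants to examine "potential AEs associated with ADAs against nanrilkefusp alfa", and patients who stop nanrilkefusp alfa for toxicity are among those who lose the later samples.

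The omission looks like an oversight. In 1.3.3 the thyroid row and the PSA/CTC row carry the same every-other-cycle footnote from cycle 4. The thyroid row was carried into 1.3.4 and the PSA/CTC row was not, and no reason is given.

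**Working it through.** The plan gives no figure to reproduce. The check compares the two tables and counts scheduled draws.

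**Does anything else restore the samples?** Protocol 8.6.2 and 8.7 set no sampling times. Footnote 1 of 1.3.1 keeps the combination schedule only in the reverse case, when pembrolizumab stops first. End of treatment follows the later of the two last doses (Protocol 4.1.2), so a switcher's End of treatment visit falls under 1.3.4, which has no ADA row. Alkaline phosphatase and lactate dehydrogenase remain covered by biochemistry.

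**Inputs.** Cycles last 3 weeks, with at most 35. The cycle 1 PSA/CTC draw is treated as baseline. *Every other cycle from cycle 4* can mean cycles 4, 6, 8… (reading A) or 5, 7, 9… (reading B).

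**Full schedule.** Reading A: cycle 3 plus cycles 4 to 34 in steps of 2, 1 + 16 = 17 post-baseline PSA/CTC draws. Reading B: cycle 3 plus cycles 5 to 35 in steps of 2, 1 + 16 = 17. Post-baseline ADA draws: cycle 2, cycle 4 and End of treatment, 3 in all. If the last nanrilkefusp alfa cycle is k, the time from day 1 of cycle k to day 1 of cycle 35 is (35 − k) × 3 weeks.

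| Last nanrilkefusp alfa cycle | PSA/CTC draws kept of 17 (A / B) | PSA response confirmable at ≥4 weeks (A / B) | Post-baseline ADA draws kept of 3 | Maximum weeks to cycle 35 |
|---|---|---|---|---|
| 1 | 0 / 0 | no / no | 0 | 102 |
| 2 | 0 / 0 | no / no | 1 | 99 |
| 3 | 1 / 1 | no / no | 1 | 96 |
| 4 | 2 / 1 | no / no | 2 | 93 |
| 5 | 2 / 2 | no / yes | 2 | 90 |
| 6 | 3 / 2 | yes / yes | 2 | 87 |
| 12 | 6 / 5 | yes / yes | 2 | 69 |

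Under reading A the cycle 3 and 4 draws are only 3 weeks apart, so the first pair at least 4 weeks apart is complete at cycle 6. Under reading B the cycle 3 and 5 draws are 6 weeks apart. The ADA draws at cycles 2 and 4 precede that cycle's dose, so neither falls after the last nanrilkefusp alfa dose.

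**PSA progression.** SAP 12.7.10 censors at the latest of PSA assessment, death and first dose. A switcher without an event is therefore censored at the last PSA before the switch, or at death if later. Confirmation ("PSA progression must be confirmed by a second value 3 or more weeks later") applies only to patients whose PSA fell on treatment. SAP 10.13.12 also accepts an unconfirmed progression when treatment discontinuation follows, but does not say whether stopping nanrilkefusp alfa alone qualifies. The same patient could be an event or censored.

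**Illustration of the bias (assumed rates).** Let a share f of mCRPC patients switch before a confirming pair is possible, have the same true response rate p as the others, and stay in the denominator. The reported rate is p × (1 − f). With p = 20%, f = 5% gives 19% and f = 30% gives 14%.

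**Numbers affected (assumed switch rate of 10% to 30%).** mCRPC: 0.10 × 51 = 5.1 to 0.30 × 51 = 15.3, about 5 to 15 patients. All indications: 0.10 × 320 = 32 to 0.30 × 320 = 96. SAP 6.1 says recruitment stopped after the August 2023 futility analysis, so the planned sizes are upper bounds.

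**The case against.** **The combination is what is being studied.** The objectives concern nanrilkefusp alfa with pembrolizumab, SAP 6.1 points to the combination schedule, and the amendment log shows ADA and prostate biomarker draws being cut to save blood. PSA change on pembrolizumab alone is arguably not combination efficacy. That would be a legitimate choice, but neither document makes it: no endpoint ends at nanrilkefusp alfa discontinuation, scans continue after the switch, and the logged cuts concern 1.3.3 only.

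**The consequences are limited.** This stands. Three of the four endpoints concern one of six cohorts, and all analyses are descriptive. Several stronger readings are tempting but not supported:
- *The four endpoints go wholly unmeasured.* Pre-switch samples count. PSA and CTC are absent after baseline only for patients who stop before cycle 3, and ADA only for those who stop in cycle 1.
- *No PSA rise before the switch can ever count.* A patient without a prior PSA decline needs no second value, and the SAP has the discontinuation rule described above.
- *PSA progression is censored at the switch.* It is censored at the last PSA value, or at death if later.
- *Patients who stop for toxicity have no ADA data.* Anyone who reaches cycle 2 dosing has a sample taken after cycle 1 exposure. Conversely, reaching cycle 4 does not give an end-of-exposure sample, because that draw is also pre-dose.

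**End of treatment ADA may come late.** For a switcher that visit follows the last pembrolizumab dose, possibly many months after nanrilkefusp alfa. This is fair, and is why the sample at the first pembrolizumab-only visit matters more.

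**Conclusion.** The gap is real and follows from the tables alone. From the switch onward, three mCRPC secondary endpoints and the nanrilkefusp alfa ADA endpoint are no longer measured, and the non-responder rules turn missing PSA and CTC values into a downward bias. Time to PSA progression has potentially informative censoring and an undefined discontinuation rule.

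The draw counts rest on 3-week cycles, scheduled samples only, and both readings of the every-other-cycle rule. How many patients are affected cannot be known from the documents: the 10% to 30% switch rate is an assumption, and 51 and 320 are ceilings. Up to about 102 weeks without these samples is the extreme case, not a typical one. Imaging is unchanged, so ORR and the radiographic endpoints are not touched. The point deserves correction because secondary endpoints are biased at little cost to repair, but it does not threaten the primary analysis.

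**What to change.** **In Protocol 1.3.4, at existing draws:**
- For mCRPC, PSA and CTC on day 1 of every other cycle, timed before pembrolizumab, since the 1.3.3 timing refers to a nanrilkefusp alfa dose that is no longer given.
- A nanrilkefusp alfa ADA sample at the first pembrolizumab-only day 1 visit, and one at End of treatment for parity with 1.3.3.

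**In the SAP:**
- Extend the reference in 6.1 to include Protocol 1.3.4.
- Where samples can no longer be collected, state the assessment window, censoring and denominators for PSA, CTC and PSA progression after the switch.
- Define treatment discontinuation in 10.13.12, including whether stopping nanrilkefusp alfa alone qualifies.
- In 12.10, base ADA incidence on patients with at least one post-dose sample.

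**Cost.** One or two extra tubes and their assays per affected visit, with no new visit. The SAP changes are wording only.

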### 1.3.5 Nanrilefusp alfa pharmacokinetic sampling

All attempts should be made to collect the samples on time.

Cycle, day	Time point (pre-dose or time after nanrilefusp alfa administration)	12 patients per indication	Rest of the patients
Cycle 1 day 1	Pre-dose to nanrilefusp alfa	X	
	30 min ( $\pm 5$ min)	X	
	1 h ( $\pm 5$ min)	X	
	2 h ( $\pm 15$ min)	X	
	4 h ( $\pm 30$ min)	X	X
	12 h ( $\pm 2$ h) (optional)	X	
Cycle 1 day 2	Pre-dose to nanrilefusp alfa (-2 h [-15 min] to 0 h)	X	X
Cycle 1 day 8	Pre-dose to nanrilefusp alfa (-2 h [-15 min] to 0 h)	X	
Cycle 1 day 9	Pre-dose to nanrilefusp alfa (-2 h [-15 min] to 0 h)	X	
	2 h ( $\pm 15$ min)	X	
	4 h ( $\pm 30$ min)	X	X
Cycle 2 day 1	Pre-dose to nanrilefusp alfa (-2 h [-15 min] to 0 h)	X	
	2 h ( $\pm 15$ min)	X	
	4 h ( $\pm 30$ min)	X	X
Cycle 2 day 9	Pre-dose to nanrilefusp alfa (-2 h [-15 min] to 0 h)	X	
	2 h ( $\pm 15$ min)	X	
	4 h ( $\pm 30$ min)	X	X
Cycle 3 day 1	Pre-dose to nanrilefusp alfa (-2 h [-15 min] to 0 h)	X	
	2 h ( $\pm 15$ min)	X	X

## 2 INTRODUCTION

### 2.1 Study rationale

The involvement of the immune system in the control of tumor growth is well accepted and immunotherapy is taking a major place in the treatment of cancers. Current cancer immunotherapies that have been investigated for their efficacy include, among others, cytokine therapy and immune checkpoint inhibition. Emerging clinical data showed that cytokine therapy is safe and feasible in the outpatient setting and can be safely combined with immune checkpoint inhibitors. We hypothesize that this combination leads to synergistic outcomes in the induction and/or maintenance of the antitumor responses by activation of both innate and adaptive cellular immune responses against tumor cells.

This basket study is planned based on results from pre-clinical studies of nanrilkefusp alfa (SOT101) and preliminary results from an ongoing clinical study of nanrilkefusp alfa (study SC103 [AURELIO-03, NCT04234113], a multicenter, open-label, phase 1/1b study to evaluate the safety and preliminary efficacy of SO-C101 [nanrilkefusp alfa] as monotherapy and in combination with pembrolizumab in patients with selected advanced/metastatic solid tumors). Study SC103 (AURELIO-03) shows that the combination of nanrilkefusp alfa and pembrolizumab can be safely administered. The safe recommended dose of nanrilkefusp alfa in combination with pembrolizumab is 12 µg/kg body weight on days 1, 2, 8, and 9 every 3 weeks, the same as for nanrilkefusp alfa monotherapy. Preliminary efficacy signals were seen both in monotherapy and even stronger in combination therapy.

### 2.2 Background

Therapy with recombinant interleukin (IL)-2, a T-cell and natural killer (NK)-cell growth factor, was one of the earliest successes in immunotherapy. IL-2 (International Nonproprietary Name: aldesleukin) was approved in some countries in the EU to treat metastatic renal cell carcinoma and by the US Food and Drug Administration (FDA) to treat metastatic renal cell carcinoma and malignant melanoma.

IL-15 is a cytokine that has many overlapping functions like IL-2, including the ability to promote antitumor responses, but with distinct advantages over IL-2. While both IL-2 and IL-15 signal through the common IL-2 receptor (IL-2R) chains  $\beta$  and  $\gamma$  (IL-2R $\beta\gamma$  or IL-15 receptor [IL-15R]  $\beta\gamma$ ) complex, which is responsible for intracellular signaling through the JAK/STAT, MAPK, and PI3K pathways in T cells and NK cells, only IL-2 engages the high-affinity IL-2R chain  $\alpha$  (IL-2R $\alpha$ ). As IL-2R $\alpha$  is expressed on regulatory T cells (Tregs), IL-15 does not induce the expansion of these immunosuppressive cells. Because IL-15 can engage IL-2R $\beta\gamma$  without engaging IL-2R $\alpha$  on Tregs, it is thought to have an improved therapeutic index compared with IL-2.

Despite the promising preclinical responses of recombinant IL-15, success in the clinical setting was limited by its short *in vivo* half-life. To date, 3 main modifications of IL-15 have been made to generate more potent soluble IL-15 agonists: 1) combining IL-15 with a soluble IL-15R chain  $\alpha$  (IL-15R $\alpha$ ) or the sushi domain of IL-15R $\alpha$ ; 2) fusing IL-15R $\alpha$  to the Fc portion of human IgG1; 3) mutating IL-15 to increase its affinity to IL-2R $\beta\gamma$ . All formulations of IL-15 agonists have demonstrated increased strength and duration of IL-15R signaling and subsequent enhanced antitumor immunity in nonclinical studies.

---

In order to make use of the enhanced biological activity of the IL-15/IL-15R $\alpha$  complex for the treatment of cancer and to overcome the need for endogenous IL-15R $\alpha$  or co-administration of IL-15 with IL-15R $\alpha$ , we engineered nanrilkefusp alfa, a fusion protein which consists of the N-terminal sushi domain of human IL-15R $\alpha$  covalently coupled via a linker of 20 amino acids to human IL-15. The biological activity of nanrilkefusp alfa stems from the function of the IL-15 component, which acts as a pleiotropic cytokine and plays a critical role in stimulating both innate and adaptive immune responses. Experimental data have indicated that the biological activity of IL-15 was enhanced when co-administered with recombinant soluble IL-15R $\alpha$ . Thus, nanrilkefusp alfa, which fuses the IL-15 component to the IL-15R $\alpha$  component, may be more potent than IL-15 alone and may benefit from an extended half-life.

Nanrilkefusp alfa promoted mobilization, expansion, and activation of human NK and CD8+ T cells in humanized mice and murine NK and CD8+ T cells in syngeneic mice. This NK- and CD8+ T-cell activation correlated with the potent anti-cancer therapeutic effects of nanrilkefusp alfa.

For detailed background information on nanrilkefusp alfa refer to the Investigator's Brochure (IB).

Pembrolizumab is a potent humanized IgG4 monoclonal antibody (mAb) with high specificity of binding to the programmed cell death protein 1 (PD-1) receptor, thus inhibiting its interaction with programmed cell death ligand 1 (PD-L1) and programmed cell death ligand 2 (PD-L2). Based on preclinical *in vitro* data, pembrolizumab has high affinity and potent receptor blocking activity for PD-1. Pembrolizumab has an acceptable preclinical safety profile and is in clinical development as an intravenous (IV) immunotherapy for advanced malignancies. Keytruda® (pembrolizumab) is indicated for the treatment of patients across a number of indications. For more details on specific indications refer to the IB.

For detailed background information on pembrolizumab refer to the IB.

The importance of intact immune surveillance function in controlling outgrowth of neoplastic transformations has been known for decades. Accumulating evidence shows a correlation between tumor-infiltrating lymphocytes in cancer tissue and favorable prognosis in various malignancies. In particular, the presence of CD8+ T cells and the ratio of CD8+ effector T cells/FoxP3+ Tregs correlates with improved prognosis and long-term survival in solid malignancies, such as ovarian, colorectal, and pancreatic cancer; hepatocellular carcinoma; malignant melanoma; and renal cell carcinoma. Tumor-infiltrating lymphocytes can be expanded *ex vivo* and reinfused, inducing durable objective tumor responses in cancers such as melanoma.

The PD-1 receptor-ligand interaction is a major pathway hijacked by tumors to suppress immune control. The normal function of PD-1, expressed on the cell surface of activated T cells under healthy conditions, is to down-modulate unwanted or excessive immune responses, including autoimmune reactions. PD-1 (encoded by the gene *Pdcd1*) is an Ig superfamily member related to CD28 and cytotoxic T lymphocyte-associated protein 4 (CTLA-4) that has been shown to negatively regulate antigen receptor signaling upon engagement of its ligands (PD-L1 and/or PD-L2).

The structure of murine PD-1 has been resolved. PD-1 and its family members are type I transmembrane glycoproteins containing an Ig-variable type domain responsible for ligand binding and a cytoplasmic tail responsible for the binding of signaling molecules. The cytoplasmic tail of PD-1 contains 2 tyrosine-based signaling motifs, an immunoreceptor

tyrosine-based inhibition motif, and an immunoreceptor tyrosine-based switch motif. Following T-cell stimulation, PD-1 recruits the tyrosine phosphatases, SHP-1 and SHP-2, to the immunoreceptor tyrosine-based switch motif within its cytoplasmic tail, leading to the dephosphorylation of effector molecules such as CD3 zeta, protein kinase C-theta, and zeta-chain-associated protein kinase ZAP70, which are involved in the CD3 T-cell signaling cascade. The mechanism by which PD-1 down-modulates T-cell responses is similar to, but distinct from, that of CTLA-4, because both molecules regulate an overlapping set of signaling proteins. As a consequence, the PD-1/PD-L1 pathway is an attractive target for therapeutic intervention in various cancers.

Therapeutic studies in mouse models have shown that administration of antibodies blocking PD-1/PD-L1 interaction enhances infiltration of tumor-specific CD8+ T cells and ultimately leads to tumor rejection, either as a monotherapy or in combination with other treatment modalities. Anti-mouse PD-1 or anti-mouse PD-L1 antibodies have demonstrated antitumor responses in models of squamous cell carcinoma, pancreatic carcinoma, melanoma, acute myeloid leukemia, and colorectal carcinoma. In such studies, tumor infiltration by CD8+ T cells and increased interferon gamma, granzyme B, and perforin expression were observed, indicating that the mechanism underlying the antitumor activity of PD-1 checkpoint inhibition involved local infiltration and activation of effector T-cell function *in vivo*. Experiments have confirmed the *in vivo* efficacy of anti-mouse PD-1 antibody as a monotherapy, as well as in combination with chemotherapy, in syngeneic mouse tumor models (see the IB).

